## 2.3 Study design

This will be an interventional study with randomized control and open label trial. A parallel-group design with pre- and post-measurements (longitudinal design) will be employed, using subjective and objective measurements with questionnaires and structured interviews. It is a single center and national project.

The study consists of five phases:

1. Screening: Screening will be conducted by the applicant and master's students enrolled in the project who are bound to medical confidentiality, using electronic patient files at the hospital. The patients will be invited to the study by their treating physician or psychologist.

2. Pre-interventional measurement (1 session within the first week, max. 60minutes):

First, the psychopathological symptoms are to be assessed in order to decide about inclusion or exclusion (with PANSS; see also inclusion criteria). In addition, the therapeutic alliance and motivation for psychotherapy are measured. In order to record moderating effects or covariables, demographics (e.g. age, gender, education, years of illness) and two additional questionnaires will be added (attitude towards recovery and the individual motives).

3. Intervention (4 sessions within two weeks, 25- 40 minutes/session):

The patients receive either four sessions of motivational interviewing (intervention group) or four sessions of supportive counseling (control group). For Details see 2.4 "Study intervention"

4. Post-interventional measurement (1 session, max. 60 minutes): At the end of the intervention the motives, the negative symptoms, the hope for recovery, well-being and the level of functioning will be measured again.

The risk of bias should be kept at a minimum. Various precautions are being taken to this end.

- The most important confounding variables are controlled to prevent a bias.
- In order to avoid selection bias, patients are randomly assigned either to the intervention group or to the control group. Randomization is carried out at a 1:1 ratio, using pre-defined random lists (using the online randomization generator: <http://www.pub-med.de/tools/zufallsgenerator>) and a block schema prepared by the principal investigator.
- Block randomization ensures that the patients are distributed in the desired proportion to the two treatment modalities. All patients are randomized only once during the entire examination period.

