### **3.2 Recruitment, screening and informed consent procedure**

Recruitment of patients will take place at the Psychiatric University Hospital Zurich in the form of ongoing recruitment by the study coordinator in the clinical setting as well as by other physicians and psychologists at the hospital. The study is presented and reminded to them in regular intervals at internal clinic reports.

The investigators will explain to each participant the nature of the study, its purpose, the procedures involved, the expected duration, the potential risks and benefits and any discomfort it may entail. Each participant will be informed that the participation in the study is voluntary and that he or she may withdraw from the study at any time and that withdrawal of consent will not affect his or her subsequent medical assistance and treatment.

The participant will be informed that his or her medical records may be examined by authorised individuals other than their treating physician.

All participants for the study will be provided a participant information sheet and a consent form describing the study and providing sufficient information for participant to make an informed decision about their participation in the study. Enough time (one to five days) will be given to the participant to decide whether to participate or not.

The formal consent of a participant, using the approved consent form, will be obtained before the participant is submitted to any study procedure.

The consent form will be signed and dated by the investigator or his designee at the same time as the participant sign. A copy of the signed informed consent will be given to the study participant. The consent form will be retained as part of the study records. The informed consent process must be documented in the patient file and any discrepancy to the process described in the protocol must be explained.

In the case of incapacity to judge or if there is doubt about the capacity to judge, a separate procedure takes place:

The study information must be explained verbally to the interested patient in any case. Handing over the written study information alone is not sufficient. The patient should be able to describe in general terms what participation in the study entails and what the patient's rights are.

If there are doubts about the patient's ability to judge, either because he/she is unable to reproduce what is contained in the study information, or because of critical comments by the health

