**3.3 Study procedures**

[figure not shown]
Time schedule

The study will last from October 2022 to September 2023.

- From October to December 2022, the study will be planned, and the ethics application will be written and submitted.
- From January, the concrete preparations will take place and
- from February 2023, the implementation will take place. The survey phase will last until August 2023.
- From August to October 2023, the study is to be evaluated, completed and the data analysed.

As can be seen in Table 2, the duration for each patient is between 13 and max. 16 days during their inpatient stay. The goal is to start with the study intervention as soon as possible after entering the psychiatric hospital.

Table 1: Study Flow Chart

**Table 2:** Overview study procedure

\* If questions / need for feedback occur after the last visit, an additional visit shall be provided

	Re-cruitment	Pre-Measurement	Intervention phase				Post-Measurement	
Visits	1 max. 30min.	2 max. 60min.	3 25- 40min .	4 25- 40min .	5 25- 40min .	6 25- 40min .	7 max. 60min.	Follow up max. 60min.
Time (days)	-3 +/-2d	0	2 +/-1d	4 +/-1d	6 +/-1d	8 +/-1d	10 +/-1d	60 +/-5d
Check with treating physician or psychologist	x							
Patient Information and Informed Consent	x							
Randomization	x							
Demographics and information about current treatment	x							
Examination of symptoms with PANSS and MATRICS		x					x	x
Control of In- and Exclusion Criteria		x						
Measurements of secondary outcome variables		x					x	
MI-Intervention (intervention group) or supportive conversations (controls)			x	x	x	x		
Possibility for patients to ask questions and give a feedback							x*	

Detailed description of the planned intervention

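### Table 2 marks randomisation 1 to 5 days before the eligibility check and baseline scales, so patients can be lost, and baseline alliance rated, after allocation

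*Combined protocol and SAP*

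**What the plan says.** **Schedule (section 3.3, Table 2).** Visit 1 is on day -3 +/-2 and lasts at most 30 minutes. It carries the marks for "Patient Information and Informed Consent", randomisation and demographics. Visit 2, on day 0, carries the marks for "Control of In- and Exclusion Criteria", the first PANSS and MATRICS tests, and the secondary outcome variables. Session 1 (visit 3) is on day 2 +/-1. The table has no row for the primary outcomes.

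**Text (section 2.3).** The pre-interventional session has the same order: "First, the psychopathological symptoms are to be assessed in order to decide about inclusion or exclusion". It continues: "In addition, the therapeutic alliance and motivation for psychotherapy are measured". Section 2.2 says only that STAR and BARS are measured before and after the intervention; no visit is named for BARS. Screening before invitation is done "using electronic patient files at the hospital".

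**Consent (section 3.2).** "The formal consent of a participant, using the approved consent form, will be obtained before the participant is submitted to any study procedure". The same section says: "Enough time (one to five days) will be given to the participant to decide whether to participate or not".

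**Blinding.** Section 2.3 opens with "This will be an interventional study with randomized control and open label trial". Later bullets in 2.3, and the part of 3.3 on expected biases, describe a single-blind study in which patients do not know their group; 2.3 adds that raters are blinded. The principal investigator prepares the block schema. No allocation concealment is described, and the person who judges eligibility at visit 2 is not named.

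**Analysis.** Section 4.1 specifies ANCOVA with the baseline value as covariate. Section 3.4 provides for replacement of withdrawn participants.

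**The concern.** Allocation is normally made once eligibility is settled and baseline is recorded, so that nothing before treatment can be influenced by the arm. Here the marks run the other way, with two consequences.

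1. **Losses after allocation.** A patient who leaves between visits 1 and 2 has been randomised but has neither baseline scores nor an outcome. One excluded at visit 2 may have some baseline scores but no post-measurement. Neither can enter the planned ANCOVA. If such losses relate to the arm, the analysed groups are no longer the randomised groups.
2. **Baseline after allocation.** Baseline STAR, the covariate for one primary endpoint, is rated when the arm has already been assigned. STAR has a clinician version (section 3.3, psychometric tests). If that clinician knows the arm, the covariate itself can be affected, and adjusting for it can carry the effect into the treatment comparison.

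The plan does not ask for post-randomisation losses to be shown by arm, so a reader of the results could not tell a harmless loss from a selective one.

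**Working it through.** **Order of events.** Visit 1 window: -3 - 2 = -5 to -3 + 2 = -1. The randomisation mark therefore precedes the day 0 check by 1 to 5 days. Visit 3 window: 2 - 1 = 1 to 2 + 1 = 3, which leaves 1 to 3 days between visit 2 and session 1. No visible text puts randomisation after the check. The Table 1 flow chart is not readable in the text available and could not be checked.

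**The plan's own figure.** Inputs from section 4.1: f = 0.25, two-sided alpha 0.05, 64 per group. With two equal groups d = 2f = 0.5. Noncentrality = f² × N = 0.0625 × 128 = 8, which gives power 0.801. The stated 128 reproduces.

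**Who could be lost at visit 2 through ineligibility?**
- PANSS: section 2.3 says it informs inclusion, but section 3.1 lists no PANSS threshold.
- Cognitive tests: section 3.1 requires very low scores in more than two tests, while section 3.3 gives two. As written, the criterion cannot be met. The two places must be reconciled.
- Age, ICD-10 diagnosis, organic disorder and previous enrolment can be known from the files screened beforehand.

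So the documents show an intent to decide inclusion at visit 2, but almost no rule that would operate there. The number lost, k, is not given and may be near zero.

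**Illustration A: losses unrelated to arm.** No bias. If each loss is replaced, k losses cost k extra recruits. If losses are not replaced and fall equally, power at d = 0.5 (two-sided t-test, no gain from the covariate) is:

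| k | analysed per arm | power |
|---|---|---|
| 0 | 64 / 64 | 80.1% |
| 4 | 62 / 62 | 78.9% |
| 8 | 60 / 60 | 77.5% |

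**Illustration B: all k losses in one arm.** Let D be the difference in mean outcome, in SD, between retained and lost patients (assumed). The shift in the unadjusted comparison is:
- with replacement: D × k / (64 + k), SE = sqrt(2/64) = 0.177
- without replacement: D × k / 64, SE = sqrt(1/64 + 1/(64 - k))

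Type I error = P(|Z + shift/SE| > 1.96). For example, k = 8, D = 1, replaced: shift = 8/72 = 0.111; 0.111/0.177 = 0.63; type I error 9.6%.

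| k | D | shift, replaced | shift, not replaced | type I error (replaced to not replaced) |
|---|---|---|---|---|
| 4 | 0.5 | 0.029 | 0.031 | 5.3% to 5.4% |
| 4 | 1.0 | 0.059 | 0.063 | 6.3% to 6.4% |
| 8 | 0.5 | 0.056 | 0.063 | 6.1% to 6.4% |
| 8 | 1.0 | 0.111 | 0.125 | 9.6% to 10.5% |
| 8 | 1.5 | 0.167 | 0.188 | 15.6% to 17.6% |

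The last row shows that the figures grow with the assumed D. They illustrate scale and bound nothing. The ANCOVA removes the part of the shift carried by the baseline score: all of it if loss acts only through that score and the model is right, none if loss is unrelated to it.

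**The case against.** The strongest reply is that almost nobody will be lost in this gap. Files are screened before invitation, there is no PANSS threshold, and the cognitive criterion cannot be met as written. Section 3.4 counts withdrawal of consent among the grounds for withdrawing a participant and then provides for replacement, so the number analysed is restored for those who leave. PANSS is a rater's interview and raters are blinded; if the person who decides eligibility is blind to the arm, exclusions on pre-treatment grounds do not bias the comparison. All of this stands, and it keeps the expected harm small. What remains is that replacement restores numbers but not the randomised comparison, that section 3.4 does not say whether a patient found ineligible counts as withdrawn, and that no text says the eligibility judge, or the clinician completing STAR, is unaware of the arm.

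Two stronger readings are tempting.

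- **That patients are randomised before they have decided to take part**, because the decision time and the gap between visits are both one to five days. The documents do not support this. Section 3.2 requires formal consent before any study procedure, Table 2 lists consent above randomisation, and patients are invited by their treating clinician, so the information may be given earlier. The equal lengths may be coincidence; when the decision time starts is not stated.
- **That the completer rule in 4.2 causes the problem and rewriting it would cure it.** A patient lost before visit 2 has no outcome under any rule. Any analysis of randomised patients with a post-measurement omits that patient too.

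**Conclusion.** The point holds as a fault in the schedule: Table 2 and section 2.3 together place allocation before the inclusion decision and before baseline alliance, and no visible text reverses this. The open question about the flow chart does not remove it; a different order there would contradict Table 2, which would still need correcting.

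The size of the harm is not established. It is zero if no one is lost and baseline ratings are unaffected, and there is no bias if losses and ratings are independent of the arm. A reader might infer that the trial will be biased, or take the type I error figures as worst cases. Neither is supported: k, D and the placement of all losses in one arm are assumptions, and larger values of D give larger figures. The open-label and single-blind statements conflict and must be reconciled, but the conflict does not show that anyone judging eligibility knows the arm.

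The correction is worth making because it removes the risk at almost no cost. Confidence is high for the order of events and low for any number attached to the harm.

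**What to change.** 1. **Table 2:** move the randomisation mark from visit 1 to the end of visit 2, after consent, confirmed eligibility and all baseline scales, with STAR and BARS named, and before session 1. State that allocation is not revealed until then. Sample size stays at 128. The cost is one table mark; the downside is that only 1 to 3 days remain to assign a therapist.
2. **Reporting:** state that every patient lost or excluded after randomisation is reported by arm with the reason. Section 7.2 already makes the reason for premature discontinuation source data, so little or nothing new is collected.
3. **Reconcile:** the open-label and single-blind statements, and the cognitive criterion in 3.1 with the two tests in 3.3. Name who judges eligibility at visit 2.

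The completer rule in 4.2 also conflicts with section 3.4, which would use the data of non-finishers where possible. That should be settled as a separate issue; it is not the remedy for this gap.

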#### Psychometric tests used in the study

Primary diagnosis at point of admittance and medical history are assessed by physicians and psychologists at PUK and documented electronically. The applicant and master's students enrolled in the project will use this available data and document them in specific study protocols. These assessments are part of standard assessments at the hospital by physicians and psychologists. For primary psychiatric diagnoses the International Classification of Diseases (ICD-10) is used.

- Psychotic symptoms are assessed with the *Positive and Negative Syndrome Scale* (PANSS). This is a structured interview, which consists of four scales measuring positive and negative syndromes of schizophrenia, their differential, and general severity of illness.
- Two cognitive tests: Letter-Number-Span (LNS), Symbol-Coding-Test (SCT) from MATRICS (Measurement and Treatment Research to Improve Cognition in Schizophrenia, Consensus Cognitive Battery; Nuechterlein et al., 2008)
- The *Brief Adherence Rating Scale* BARS (Byerly et al, 2008) is a brief, pencil-paper, clinician-administered adherence assessment instrument. It consists of 4 items: 3 questions and an overall visual analog rating scale to assess the proportion of doses taken by the patient in the past month (0%–100%).
- The therapeutic relationship will be evaluated with the *Scale to Assess Therapeutic Relationship* STAR (McGuire-Snieckus et al., 2007). The patient (STAR-P) and clinician scales (STAR-C) each have 12 items comprising three subscales: positive collaboration and positive clinician input in both versions, non-supportive clinician input in the patient version, and emotional difficulties in the clinician version.
- Motivation for psychotherapy will be measured with the *Fragebogen zur Erfassung der Psychotherapiemotivation* (FPTM; engl: "Questionnaire to measure the motivation for psychotherapy") by Schulz, Nübling und Rüdell (1995), a 4-point Likert-scale with 39 items.
- Self-efficacy is measured with the German version of the *General Self-Efficacy Scale* (GSE) by Schwarzer & Jerusalem (1995), an instrument that has been proved with a sample of more than 19'000 persons in 25 countries and shows good psychometric properties.

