### **2.2 Primary and secondary endpoints**

Primary endpoints are the therapeutic alliance as assessed with the *Scale to Assess Therapeutic Relationship STAR* (McGuire-Snieckus et al., 2007) and adherence to treatment as measured with the *Brief Adherence Rating Scale BARS* (Byerly et al., 2008). These variables will be measured before and after the study intervention or control intervention.

Secondary endpoints include changes in symptom severity as assessed with the *Positive and*

*Negative Symptom Scale PANSS* (Kay et al., 1987), as well as the motivation for psychotherapy (measured with the German version of the *Questionnaire to measure the motivation for psychotherapy* by Schulz et al., 1995) and self-efficacy (measured with the *General Self-Efficacy Scale* by Schwarzer & Jerusalem, 1995). All secondary variables will be measured before and after the study intervention or control intervention.

As this study (risk category A) does not include drugs or other medical products and patients are hardly exposed to any more risks than in routine clinical care, no safety endpoints are defined.

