### **3 STUDY POPULATION AND STUDY PROCEDURES**

#### **3.1 Inclusion and exclusion criteria, justification of study population**

As the aim of the study is to improve psychotherapeutic treatment in the acute phase of psychosis, the inclusion of patients suffering from this disorder is necessary and cannot be studied in healthy people.

We will recruit newly admitted inpatients from the Psychiatric University Hospital with a diagnosis of a psychotic spectrum disorder (schizophrenia, schizoaffective disorder, acute psychotic

disorder, psychosis not otherwise specified, bipolar disorder with psychotic features, major depression with psychotic features). Patients are recruited within the first three days of hospitalization to test psychotherapeutic interventions in the acute phase of illness.

Patients fulfilling all of the following inclusion criteria may be enrolled in the study:

- Informed consent as documented by signature
- Male and female patients from PUK inpatient units between 18 and 65 years of age
- ICD-10 diagnosis of psychosis (F2) meeting DSM-IV criteria
- Fluent in German and able to understand the instructions

The presence of any one of the following exclusion criteria will lead to exclusion of the participant:

- Organic schizophrenia-like disorder (ICD: F0.6)
- Cognitive impairments: strongly below average values in more than two cognitive tests (percentage rank < 5)
- Drug or alcohol abuse during treatment
- Previous enrolment in the current study
- Enrolment of the investigator, his/her family members, employees and other dependent persons.
- During study: Complete stop of taking antipsychotic medications without the consent of the attending physician.

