## 4 STATISTICS AND METHODOLOGY

### 4.1. Statistical analysis plan and sample size calculation

Hypothesis 1: Four sessions of motivational interviewing for newly admitted acute patients (within the first 7 days of hospitalization) improve the therapeutic alliance and the adherence for treatment compared to supportive counseling.

Statistical analysis for hypothesis 1: To apply the statistically most sensitive test, we will use an ANCOVA to analyze the treatment effect of motivational interviewing compared to supportive counseling, with baseline values used as covariates.

Hypothesis 2: Four sessions of motivational interviewing for newly admitted acute patients decreases symptom severity compared to supportive counseling.

Statistical analysis for hypothesis 2: We will use an ANCOVA to analyze the treatment effect of motivational interviewing compared to supportive counseling, with baseline values used as covariates.

Hypothesis 3: Patients show higher motivation to seek psychotherapeutic treatment and have a higher self-efficacy expectation after leaving the inpatient stay, when they received an intervention with motivational interviewing compared to supportive counseling.

Statistical analysis for hypothesis 3: We will use an ANCOVA to analyze the treatment effect of motivational interviewing compared to supportive counseling, with baseline values used as covariates.

Additional calculations: We also want to investigate how the number of hospitalization days and the severity of symptoms at the beginning of the intervention have an influence on the therapy outcome. We calculate this with a multiple regression with days of hospitalization and/or the PANSS total score as independent variables. The treatment outcome is defined as the delta between symptoms before and after the intervention and serves as dependent variable.

General statistical considerations: We will use routine procedures of data processing and use data transformation if necessary (in case of non-normal distribution). Standard statistical calculations will be computed. The level of significance will be set to  $p < 0.05$  (two tailed). Effect sizes will be calculated for significant results. The IBM® SPSS Statistics® statistical software as well as the program R will be used.

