Sample size justification: Comparable studies found effect sizes that were moderate (Cohen's  $d = 0.3 - 0.5$ ). An effect sizes of  $f = 0.25$  will require us to recruit at least 64 patients per group to achieve 80% power and to detect such an effect with reasonable certainty at an alpha level of 0.05. We therefore plan to include a minimum of  $N = 128$  patients (calculated with G\*Power 3.1).

Analysis population: There is only one analysis population for all hypothesis. For inclusion criteria see chapter 4.1.

Analysis of gender differences: Analyses of gender differences are not planned because there is no research evidence to suggest that gender may be a determining variable. However, it is planned to conduct a group comparison between patients who benefit strongly from MI and those who benefit little, and to investigate possible discriminatory factors as part of this.

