#### 4.2. Handling of missing data and drop-outs

All patients who completed the study will be taken into analysis. All collected data will be checked at each study assessment, and missing data will thus be avoided as much as possible. If missing data nevertheless does occur, data has to be excluded.

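### The plan has no rule for baseline BARS, a primary endpoint, when a patient had no doses due before admission, and its missing-data rule can then cost power in the BARS analysis

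*Combined protocol and SAP*

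**What the plan says.** Section 2.2 names BARS and STAR as the primary endpoints and adds: "These variables will be measured before and after the study intervention or control intervention". Section 3.3 (psychometric tests) describes BARS as three questions plus a visual analogue rating, from 0 to 100%, "to assess the proportion of doses taken by the patient in the past month".

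Section 3.1 states: "Patients are recruited within the first three days of hospitalization to test psychotherapeutic interventions in the acute phase of illness". Section 2.3 places the pre-measurement within the first week. None of the four inclusion criteria mentions a prescription, earlier treatment or an earlier episode. The only medication criterion concerns stopping antipsychotics altogether during the study.

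Section 4.1 tests hypothesis 1 by ANCOVA "with baseline values used as covariates" and adds: "There is only one analysis population for all hypothesis". Section 4.2 first says that all completers are analysed, and then: "If missing data nevertheless does occur, data has to be excluded". No section says how BARS is scored when no doses were due in the past month.

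**The concern.** A proportion of doses needs doses due as its denominator. With recruitment in the first three days and baseline in the first week, the past month at baseline lies mostly before admission. An eligible patient who had nothing prescribed in that period has either no denominator or one made up of a few ward days. For the same patient a rater could leave the item blank, enter 0% because nothing was taken in most of the month, or enter 100% because every ward dose was taken. The plan excludes none of these, and they lead to different analyses.

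If the item is blank, the ANCOVA has no covariate value and the exclusion rule in 4.2 removes the data. Section 3.4 replaces withdrawn participants, but a patient who completes the study with an undefined baseline has not withdrawn and is not replaced. At stake are the power of one primary analysis and the population it describes: with these patients gone, the BARS result covers only those already prescribed medication before admission.

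**Working it through.** **Inputs from the documents.** f = 0.25, 64 per group, N = 128, 80% power, alpha 0.05 (4.1, sample size justification); two-tailed tests (4.1, general considerations); 1:1 allocation (2.3); ANCOVA with baseline as covariate (4.1). **Assumed:** the share u of patients whose baseline BARS is blank and excluded. The documents give no figure, so a range is shown.

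**Step 1: reproduce the plan's figure.** Noncentral F test with numerator df = 1, denominator df = N − 3 (two groups, one covariate) and noncentrality λ = f² × N. At N = 128, λ = 0.0625 × 128 = 8.0 and power = 0.801. The smallest N reaching 80% is 128, with or without the covariate's degree of freedom. The stated sample size is correct and has no reserve.

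**Step 2: power if a share u is excluded.** Remaining N = 128 × (1 − u), rounded. Enrolment needed to keep 128 evaluable = 128 / (1 − u), rounded up.

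| u (assumed) | Patients lost | N left | λ = 0.0625 × N | Power | Enrolment for 128 evaluable |
|---|---|---|---|---|---|
| 0 | 0 | 128 | 8.00 | 0.80 | 128 |
| 5% | 6.4 | 122 | 7.63 | 0.78 | 135 |
| 10% | 12.8 | 115 | 7.19 | 0.76 | 143 |
| 20% | 25.6 | 102 | 6.38 | 0.71 | 160 |
| 30% | 38.4 | 90 | 5.63 | 0.65 | 183 |

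**Step 3: compare ways of handling the affected patients.** Simulation with 64 per arm, d = 0.5 and 10 to 30% of patients affected, whichever arm they are in. Their outcomes are assumed observed, with the same treatment effect. The correlation between baseline and outcome is also assumed. Approximate power:

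| Handling | Correlation 0 | Correlation 0.3 to 0.5 |
|---|---|---|
| Exclude | 0.66 to 0.75 | 0.68 to 0.86 |
| Random 0% or 100% entered | 0.79 to 0.80 | 0.81 to 0.86 |
| Constant plus indicator | 0.79 | 0.82 to 0.88 |

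Exclusion loses power because it loses patients. Arbitrary scores left the treatment estimate unbiased and only diluted the adjustment. Constant plus indicator keeps every patient and most of the adjustment.

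**Step 4: bias.** Whether doses were due before admission is settled before allocation. Baseline is rated before the first session, by raters who are to be blinded (2.3). Neither exclusion nor arbitrary scoring on this ground should differ by arm.

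**The case against.** The strongest reply is that this is only a gap in scoring instructions. Several parts of it stand.

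- Exclusion follows only if the item is left blank. Section 4.2 excludes data, not expressly patients, and opens by taking all completers into analysis.
- A patient started on medication at admission has a short denominator, not an empty one. The criterion on stopping antipsychotics presupposes that participants generally take them. Nor does a first episode, or a diagnosis of acute psychosis, mean that nothing was prescribed.
- Section 3.3 does not reproduce the BARS questions, so whether the instrument has its own rule for this case cannot be checked here. That the doses are prescribed doses is implied by the word proportion, not written.
- Adherence has meaning only where treatment is prescribed, and section 2.4 presents non-adherence to antipsychotics as the problem. Some narrowing of the BARS result is therefore natural.

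A reader might also infer that these patients drop out of STAR and PANSS, because there is a single analysis population. The documents do not establish that. Section 4.1 ties the population to the inclusion criteria, not to complete data on every scale, so deletion across endpoints is only one possible reading.

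The reply does not remove the core gap. A few ward days are not the past-month measure that the protocol describes, a blank remains a permitted answer, and the only stated rule for a blank is exclusion from a primary analysis with no power to spare.

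**Conclusion.** The point holds for BARS as a matter of power and reach. A randomised patient with no doses due before admission can be lost from the BARS ANCOVA or carry an arbitrary baseline, and the plan does not say which. If 5 to 30% were excluded, power would fall from 0.80 to between about 0.78 and 0.65. That range rests on two assumptions outside the documents: the affected share, and that every such baseline is left blank and removed.

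Three stronger conclusions may tempt a reader but are not supported: that untreated or first-episode patients will certainly be dropped, since blank is one of three possible entries; that every trial result is affected, since the step to the other scales is conjecture; and that arbitrary scores make the covariate worthless or bias the comparison, since they weaken the adjustment and leave the planned power at about 0.79 or above.

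It is still more than a missing detail. A cheap alternative retains these patients, whereas the stated rule would discard their data.

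**What to change.** - **Section 3.3:** record baseline BARS as *not applicable*, neither 0% nor 100%, when no antipsychotic doses were due before admission. Derive this from the treatment information already collected at visit 1 (Table 2), making sure that it covers prescriptions before admission.
- **Section 4.1:** keep these patients in the BARS ANCOVA by setting their baseline to a constant and adding a *no prior prescription* indicator. Under randomisation this is valid for a baseline covariate.
- **Section 4.2:** replace the exclusion rule for this case, and state that a missing or not-applicable BARS affects the BARS analysis only, never STAR, PANSS, FPTM or GSE.
- **Reporting:** give the number not applicable per arm at baseline and at post-measurement. The indicator repairs the baseline only. It does not repair a post-measurement BARS that is undefined or rests on ward doses alone, so readers need to see how many there are.

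The cost is one covariate (one degree of freedom), a derived flag and a few sentences, with slightly less baseline adjustment in the flagged patients. No eligibility or treatment rule changes.
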